## **Section 2.0 Introduction:**

### **2.1 Myeloma relapse is the main challenge post autologous hematopoietic Stem cell transplant (AHSCT)**

Multiple Myeloma (MM) is a hematologic malignancy with a rising incidence in the US (about 30,000 cases newly diagnosed per year and 12,000 related myeloma deaths per year). Unfortunately, myeloma is considered incurable despite widening available standard therapies. New and innovative approaches are needed to improve the outcomes of this growing disease. AHSCT has significantly improved disease free and overall survival (OS) for patients with MM. However, relapses continue to limit long term survival of these patients. The efficacy of AHSCT as a treatment modality has relied mainly on the hope that high dose chemotherapy will eradicate the resistant tumor clones that survived standard chemotherapy. This paradigm has not changed in more than 30 years. Unfortunately, the same intensive preparative transplant regimen that overcomes resistance to standard dose chemotherapy, depletes various immune cells as well as compromises their function, increasing the risk for serious infections from various agents as well as potentially increasing the risk of myeloma relapse post-transplant. Advances in modifying the chemotherapy preparative regimen and supportive care have resulted in less transplant related morbidity and mortality, but no improvement in relapse rates. Attempts at improving AHSCT efficacy by tumor cell purging, CD34 selection or switching the preparative regimen have not been successful. Therefore, new interventions are needed to improve autologous transplant outcomes.

### **2.2 High dose chemotherapy and autologous peripheral blood stem cell transplant can be a favorable vaccine platform for multiple myeloma.**

The state of minimal residual disease and abundance of homeostatic cytokines (IL-7 & IL-15) can make the early phase post AHSCT a favorable platform for vaccine response. The recovery phase of lymphopenia enhances tumor vaccine responses in multiple animal models. Mitchell et al. has demonstrated a favorable immune response to PP65 pulsed dendritic cell vaccine given during chemo induced lymphopenia in patients with glioblastoma. Sampson et al. showed that greater chemotherapy-induced lymphopenia enhances tumor-specific immune responses that eliminate EGFRvIII-expressing tumor cells in patients with glioblastoma. However, studies that tested early vaccine responses post AHSCT showed poor immune responses, which reflects the immune suppression state in the first year post AHSCT.

### **2.3 Immune reconstitution after AHSCT.**

Today's AHSCTs are almost all done with G-CSF mobilized PBSC (G-PBSC), rather than bone marrow grafts based on faster engraftment, decreased risk of infections and days of hospitalization. Early hematopoietic reconstitution of white blood cells, hemoglobin and platelets occur within the first two weeks post AHSCT. However, there is a substantial delay in reconstitution of the non-granulocytic immune components. B-lymphocytes (B-cell) recover to normal numbers within 2-4 months. Natural killer cells (CD56+3- or CD16+3- NK) reached normal values within one month post-transplant. Total T-lymphocyte (T-cell) CD3+ reconstitution occurs within 2-4 months post AHSCT. All patients showed a low CD4/CD8 ratio during the first year post transplant, due both to low numbers of CD4+ cells and elevated numbers of CD8+ cells. The low number of CD4+ cells was due to a persistently low level of naive CD4+CD45RA+ cells. While a high proportion of the CD8+ cells displayed a phenotype compatible with activated T-cells (CD8+DR+) up to 10 months after AHSCT. This seems to be secondary to the intrinsic difference between CD4 versus CD8 regeneration pathways post intensive chemotherapy. CD4 regeneration post intensive chemotherapy is more dependent on thymic function, which starts to regress even in young adults. Therefore CD4 reconstitution post AHSCT is mainly dependent on expansion of mature T-cells in the graft. A clear global

suppression of T-cell proliferative, and cytokine release in response to mitogenic agents *in vitro* has been observed in the first 6-12 months post AHSCT.

#### 2.4 Antigen specific immune reconstitution

Riemer et al. evaluated the antigen specific humoral immune response post AHSCT in 38 patients. He found that IgG antibody titers against measles, mumps, rubella, and polio were present in almost all patients pre-transplant and during 12 months post-transplant, indicating persistent humoral immunity. Svane et. al. evaluated the antigen specific cellular immune responses post AHSCT in breast cancer patients. Peripheral blood was collected from five breast cancer patients at serial time points in connection with chemotherapy treatment and in a follow-up period of 1 year. The frequencies of CD8 and CD4 T-cells responsive to cytomegalovirus (CMV), varicella zoster virus (VZV), and tetanus in antigen-activated whole blood were determined by flow cytometric analysis of CD69, (intra-cellular) TNF $\alpha$ , and IFN $\gamma$  expression. Mononuclear cells were labeled with PKH26 dye and the CMV, VZV, and tetanus toxoid-specific proliferation of T-cell subpopulations was analyzed by flow cytometry. In none of the patients did the treatment result in loss of overall T-cell reactivity for any of the antigens. Prior to chemotherapy 5/5 patients possessed TNF expressing T-cells specific for CMV, 4/5 for VZV, and 3/5 for tetanus. One year after stem cell transplantation all patients possessed TNF expressing T-cells specific for CMV, VZV and tetanus. The highest percentages of cytokine responding T-cells were seen after stimulation with CMV antigen. **In general, the lowest antigen specific immune reactivity (close to zero) was measured in G-CSF-mobilized blood at the time of leukapheresis.** Despite a continuously reduced CD4 to CD8 ratio after transplantation, recovery of antigen specific CD4 T-cells usually occurred prior to CD8 recovery and often to a higher level. This study demonstrated that natural as well as vaccine-induced specific immunity established prior to AHSCT can be regained after stem cell transplantation.

#### 2.5 The impact of post AHSCT immune suppression on risk of infections:

The risk of viral infections is higher in the first year post AHSCT. Varicella zoster virus VZV seems to be the main one, with a risk of 23-50%. The risk of VZV infections was higher when CD4<200/ $\mu$ l, and CD8<800/ $\mu$ l. Patients who met both of these predictors had a VZV risk of about 48% at one year. Other less common infections include CMV. Wingard et. al. in 1988 reported a 45% rate of CMV infections in 165 patients post auto transplant (based on a rise in CMV antibody titer). However, the rate of CMV pneumonia in that study was 2%. Kadakia et. al. reported on human herpes virus 6 (HHV6) viral infections in the first year post autologous transplant. By using direct viral isolations, HHV6 DNA, and HHV6 antibody titer testing, they could detect active HHV6 infection in 10/11 autologous transplant patients. Furthermore there was a 55% association between HHV6 isolation and sinusitis ( $P=.002$ ). The risk of CMV, VZV, parainfluenza and bacterial infections were all increased in CD34 selected AHSCT compared to standard AHSCT, based on the excessive immune suppression post-transplant caused by T-cell depletion.

#### 2.6 The impact of post AHSCT immune suppression on the risk of cancer relapse:

There is no clear direct evidence to link the post AHSCT immune suppression, slow numerical and functional T-cell recovery to rates of relapse. However, animal models and clinical data strongly suggest a link between immunosuppression and occurrence/progression of cancer. Furthermore, retrospective studies and one prospective study in AHSCT suggest that such link exists.

Animal studies of gene-targeted and lymphocyte subset-depleted mice were used to establish the relative importance of NK and NK1.1+ T (natural killer T, NKT) cells in protecting against tumor initiation and metastasis. In these models, CD3+ NK cells were responsible for rejection and

protection from metastasis of chemically induced (methylcholanthrene MCA) tumor. Similarly Rag2-/- mice (no T-cells, and B cells) showed increased susceptibility to chemically MCA induced tumors. Studies of T-cell receptor deficient mice demonstrated a non-overlapping role of  $\gamma\delta$  T-cells and  $\alpha\beta$  T-cells in blocking the formation and progression of chemically induced tumors. These studies seem to suggest that  $\gamma\delta$  T-cells act to inhibit initial tumor formation, while  $\alpha\beta$  T-cells directly inhibit tumor progression by using their cytotoxic mechanisms to kill tumor cells.

Clinical studies have shown that the high-grade density of CD8+ T-cells in cancer cell nests correlated with prognosis. The presence of tumor infiltrating T-cells (TILs) was able to predict a better survival as an independent prognostic factor in various types of cancers including colon cancer, esophageal cancer, oral squamous cell carcinoma, breast cancer, ovarian cancer, and malignant melanoma. Other studies have shown a similar positive correlation between NK cell infiltration and the survival for gastric cancer, colorectal cancer, and squamous cell lung cancer.

Increased relative risk for various types of cancers has been observed in immunosuppressed solid organ transplant recipients that have no apparent viral origin. Information on 5692 Nordic recipients of renal transplants in 1964–82 was linked to the national cancer registries in 1964–86 and to population registries. Significant overall excess risks of two-to-five-fold were seen in both sexes for cancers of the colon, larynx, lung and bladder, and in men for cancers of the prostate and testis. Notable high risks ranging from 10-30 fold above expectations, were associated with cancers of the lip, skin (non-melanoma), kidney, endocrine glands, non-Hodgkin's lymphoma, and in women with cancers of the cervix and vulva–vagina. Additionally, there have been case reports of growth and flare up of epithelial cancers in chronic lymphocytic leukemia (CLL) patients after the use of nucleoside analogs fludarabine or 2-chlorodeoxy adenosine (2CdA). Allogeneic bone marrow transplants have been associated with increased risk for squamous cell carcinoma of the buccal cavity and skin.

In AHSCT patients, the group from Mayo clinic has retrospectively evaluated the role of early lymphocyte count recovery post-transplant. In multiple reports, they found that absolute lymphocyte count ALC of 500/ $\mu$ l on day 15 post AHSCT correlated with improved overall and disease free survival in patients with Hodgkin's lymphoma, NHL, acute myeloid leukemia, multiple myeloma, amyloidosis, and breast cancer. Porrata et al reported one prospective study on 50 NHL patients undergoing AHSCT, confirming the same above observation. More recently peripheral blood absolute monocyte count (AMC) has been used as a surrogate marker of tumor microenvironment immune suppression. Porrata et al. showed a correlation between AMC excess at day 15 post-transplant with risk of relapse and low PFS. He showed that day+ 15 ALC/AMC ratio > 1.0 correlated with better survival. Furthermore, he demonstrated that the recovery of ALC and AMC at day 15 post AHSCT correlated with the numbers of these cells in the autologous graft.

The value of immune recovery was further highlighted in a recent report that looked at immune signatures associated with improved PFS and OS for myeloma patients treated with AHSCT. In this study, MM patients underwent comprehensive immune profiling (IP) in peripheral blood and had the marrow tested for MRD before and approximately 100 days after AHSCT. It was found that higher  $\gamma\delta$  T-cell counts post-AHSCT correlated with improved 2-year PFS and OS. Furthermore, the higher CD4+ central memory (CM) cell counts post-AHSCT were associated with improved 2-year OS but not PFS. The higher  $\gamma\delta$  T-cell and CD4+ CM-cell count associations were primarily observed in MRD-negative patients post-AHSCT and in patients not receiving maintenance therapy.

Collectively these studies suggest that high ALC and low AMC on day 15 post AHSCT are markers of accelerated immune recovery, and lower immune suppression, resulting in lower risk of relapse and better long-term survival.

### 2.7 The autologous graft is enriched with immune suppressive cells:

One of the immune suppressive cellular elements enriched in the G-PBSC grafts are regulatory T cells (T-reg). These CD4+CD25hi T-reg is a specialized subset of T-cells that act to suppress immune activation, and thereby maintain immune tolerance to self. FOXP3 is thought to be a characteristic marker for T-reg (a master transcriptional regulator in the development and function of regulatory T-cells). Seddiki et al. showed that expression of CD4+CD25+CD127low phenotype gave an accurate estimation of T-reg cell numbers and correlated well with FOXP3 expression. The bone marrow is an important reservoir for functional CD4+CD25hi T-reg. G-CSF mobilizes T reg from the bone marrow to the peripheral blood through down regulation of bone marrow CXCL12, a ligand for CXCR4 receptor expressed on the surface of T-reg. Ruttella et al. showed that *in vivo* exposure to G-CSF induced suppressor T-cells with a peculiar cytokine profile (IL-10 high, TGF- $\beta$ 1 high, IL-2 low, IL-4 low), and suppression of antigen-driven proliferation. A clinical trial evaluating the role of AHSCT in juvenile idiopathic arthritis demonstrated an accelerated recovery of CD4+CD25hi T-reg in peripheral blood post-transplant. This phenomenon correlated with the clinical quiescence of the autoimmune process. *In vitro* depletion of these T-reg from peripheral blood samples post-transplant partially corrected the T-cell dysfunctional state. Early after AHSCT, T-reg expansion occurs through homeostatic proliferation from the G-PBSC graft rather than through thymic differentiation.

Another immune suppressive population abundant in the G-PBSC grafts is immature monocytes. Fraser et al. showed an increased proportion of CD14+ monocytes in G-PBSC grafts. Majority of these monocytes were immature, expressed low CD14, had surface bound IL-10, and induced significant T-cells suppression *in vitro*. Activation of STAT3 pathway and expression of FAS ligand are possible mechanisms of their immunosuppressive phenotype. G-CSF mobilized immature monocytes are recruited to the tumor microenvironment, where their phenotype is further modified to become myeloid suppressor cells (MDSC). These MDSCs are usually CD33+, CD11b+, HLA-DR low and CD15+-.

As mentioned above Saven et al. noticed the lowest level of antigen specific T-cell immune responses in G-PBSC grafts. The abundance of immune suppressor cells in G-PBSC grafts raises concern about their *in vivo* effect on the immune recovery post-transplant.

### 2.8 The effect of T-reg on T-cell homeostatic expansion *in vivo*

In an autoimmune disease animal model, Shen et al. demonstrated that T-reg inhibited homeostatic proliferation of adoptively transferred T-cells, reduced their survival, and reduced their functional differentiation into cytokine producing effector/memory T-cells. Eventually these T-reg prevented the development of clinical autoimmune disease. A similar observation of enhanced T-reg recovery was made by Alexander et al. in patients with refractory systemic lupus erythematosus (SLE) who underwent AHSCT. Collectively the above data offer a possible explanation for the lack of robust T-cell homeostatic expansion post AHSCT. Therefore, in the absence of immune suppressor cells (no G-CSF), chemotherapy induced lymphopenia can stimulate significant *in vivo* expansion and activation of donor derived lymphocyte infusions both in animal models and human clinical trials.

### 2.9 *In-vivo* depletion/modulation of immune suppressive cells improves anti-tumor immune response:

Kline et al. demonstrated that depletion of T-regs enhanced *in vivo* expansion of adoptively transferred tumor specific T-cells, increased their cytokine secretion and their ability to eradicate pre-injected subcutaneous tumors in RAG2-/ (lymphocytes deficient) B16 melanoma animal model. To simulate a transplant model, similar results were observed when C57BL/6 (immune intact) mice irradiated and received adoptive transfer of total or T-reg depleted splenocytes. Collectively the above data showed that T-reg depletion not only enhanced T-cell homeostatic expansion, but also improved their ability to eradicate tumors. Jennifer Ko et al. demonstrated that sunitinib dropped the proportion of MDSC and T reg in the peripheral blood of renal cancer patients, as well as improved T-cell immune function. The use of monoclonal antibodies (CD33 or CD15) for *in vitro* purging of myeloid leukemic cells from PBSC grafts have been attempted before in clinical trials. However, significant delays in neutrophil and platelet engraftment post-transplant have prevented further development of this approach.

## 2.10 Feasibility of CD34+ selection for clinical applications

The feasibility of CD34+ hematopoietic stem cell selection in AHSCT was demonstrated in the late 90s as a strategy of purging the graft from cancer cells. This approach was tested in a large randomized phase III MM trial and shown to be safe, however there was no improvement in PFS or OS. CD34+ stem selection using the immune-magnetic bead approach is now FDA approved allogeneic stem cell transplant in acute myeloid leukemia. Previously completed phase II trial demonstrated feasibility of engraftment with as low as 2.0 million x 10^6/Kg body weight CD34+ selected stem cell graft for patient with hematologic malignancy.

[figure not shown]
Therefore, combining a pre G-CSF peripheral blood mononuclear cells (PBMC) pheresis product (autologous DLI) with CD34+ selected stem cells may produce a graft with minimum immune suppresser cells, enhanced immune reconstitution and vaccine immune response post AHSCT.

## 2.11 Preliminary data:

### **2.11.1 - G-CSF mobilized grafts are enriched with myeloid derived suppressor cells MDSCs.**

A- We have evaluated the proportion of MDSC in G-PBSC graft samples and compared them with healthy donor's peripheral blood. As shown below in **Figure 1** (first two columns on the left), the proportion of CD33+/HLA DR low, CD14+/HLA DR low, CD14 low/side scatter high population (immature monocytes), were all higher in the G-PBSC graft compared with healthy donor blood samples (six patient samples). While all the CD33+/HLADR low cells were positive for CD11b, a proportion of these MDSCs were positive for CD15 (data not shown). We demonstrated the *in vitro* feasibility of depleting MDSCs using CD33/15 Miltenyi's magnetic beads (third column from the left showed the depleted graft), while the fourth shows the positively selected population.

**Figure 1**

[figure not shown]

### 2.11.2- Depletion of T-regs and or MDSC led to improved T-cell proliferation, in response to an allogeneic mixed lymphocyte reaction.

We performed a standard one way mixed lymphocyte reaction (MLR) with responder G-PBSC graft cells ( $1 \times 10^5$  cells) co-cultured with a similar number of irradiated (2500 rads) allogeneic stimulator PBMC for 6 days in a round bottomed 96-well microtiter plates in 37° humidified 5% CO2 incubator. The cells then were pulsed with 2  $\mu$ Ci of H-thymidine for 16 hours, then harvested and counted in a beta scintillation counter. G-PBSC graft samples (six patients) were divided to 5 groups: (1) un-manipulated G-PBSC graft sample, (2) CD25 depleted, (3) CD33/CD15 depleted, (4) CD25 enriched, (5) CD33/CD15 enriched. Controls included: (1) patients' own pre G-CSF PBMC sample MLR (2) a healthy donor MLR, and (3) G-PBSC effector cells only with no targets. We observed an increase in proliferation of CD25 or CD33/15 depleted G-PBSC graft sample over un-manipulated G-PBSC graft in 6 patients, while CD25 or CD33/15 enriched groups in all

the patients had very little reaction as shown in the **Figure 2** below. Each bar shows the average counts per minute reflecting  $^3\text{H}$ -thymidine uptake for patients in that group.

## **Section 3.0 Eligibility Criteria:**

### **3.1 Inclusion Criteria**

1. Age  $\geq$  19 years to 70 years old at time of study entry (consent)
2. Diagnosis of Multiple Myeloma (MM) as per updated International Myeloma Working Group (IMWG) criteria.
3. Must have received bortezomib, lenalidomide and dexamethasone (VRd) as a form of induction therapy pre-AHSCT (use of cyclophosphamide, bortezomib and dexamethasone may be allowed for up to 2 weekly doses before initiation of VRd induction, if necessary clinically for cytoreduction)
4. Able to understand and sign a consent form.
5. Creatinine clearance equal or  $>$  60 ml/min (calculated)
6. Ejection fraction equal or  $>$  50% before admission for transplant as per institutional standards. Patients with coronary heart disease (recent myocardial infarctions, angina, cardiac stent, or bypass surgery in the last 6 months or arrhythmia) need to be cleared by cardiology as per institutional BMT standards.
7. Total bilirubin  $\leq$  2.5 times the upper limit of the institutional normal values, and total AST (SGOT) and ALT (SGPT)  $\leq$  2.5 times the upper limit of the institutional normal values.
8. FVC, FEV1 or DLCO equal or  $>$  50% predicted before admission for transplant as per institutional standards. Patients on home oxygen are not allowed on the protocol.
9. No more than 6 months of pre-transplant MM chemotherapy is allowed (from the date of the start of the induction therapy).
10. KPS  $\geq$  70% or ECOG 0-2.
11. Must be eligible to receive Melphalan dose of 200mg/m^2
12. A female of child-bearing potential, must have two negative urine pregnancy test results at time of eligibility testing and prior to GCS-F pre-transplant as a way of ensuring safe transplant planning.

### **3.2 Exclusion Criteria**

1. Participation in another clinical study with an investigational product during the last 28 days.
2. Prior stem cell transplant (either autologous or allogeneic)
3. Creatinine clearance  $<$  60 ml/min (calculated)
4. Subjects who failed to achieve  $\geq$  PR to induction therapy (i.e. VRd) and required salvage induction prior to AHSCT.
5. Documented central nervous system or extramedullary disease.
6. Significant organ dysfunction deemed to carry inappropriate risk for AHSCT.
7. Intention or plans for cyclophosphamide mobilization.
8. Known allergic reactions after previous tetanus diphtheria vaccination or had a condition of Guillain Barre Syndrome (GBS)
9. Known active hepatitis B, C or HIV infections on initial assessment.
10. Enrollment on any other transplant related protocols.

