## **Section 4.0 Registration Procedure:**

The date of enrollment is the date of consent. However, all eligibility criteria do not need to be met until the date of the first study related treatment.

All subjects need to sign the consent form in order to enroll on the study. They will receive a copy of the consent form. In case of any issues, the treating physician or PI should be called for clarification. The subject will be registered as described below in section 4.2.

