#### **4.3 Randomization**

The protocol will randomize subjects to two subsequent arms (10 subjects per arm): group 1 will get a CD34+ selected graft + autologous DLI on day+7, while group 2 will get standard G-CSF mobilized graft only.

The process of a 1:1 randomization between the experimental and control arms. During the registration procedures, study personnel are provided the randomization assignment from the the

IIT Office project coordinator. The 1:1 randomization will be conducted using blocked randomization with blocks of size 2 or 4.

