##### **5.1.1 Pre-transplant Tetanus Vaccine**

Vaccination can start whenever the subject is in reasonable physical condition to move forward to AHSCT (VRd 3-6 cycles) with a minimum of partial response by IMWG, and at least 2 weeks since the last doses of bortezomib, lenalidomide or dexamethasone. Tetanus (without pertussis) is given pre-transplant as an intramuscular injection. Tetanus vaccination will be documented in the medical record per usual clinical practice. Data needed for the study data set will be recorded from this information.

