### **5.6 Removal from the study**

Subjects who for whatever reason do not meet the cardiac ejection fraction, pulmonary function test requirement or develop significant organ dysfunction before the transplant admission will be removed from the study.

The investigator will withdraw a subject from the study treatment whenever:

1. Continued participation is no longer in the subject's best interests. Reasons for discontinuing treatment may include the occurrence of a SAE or an inter-current illness. These subjects will be taken off treatment and followed according to the study calendar.
2. The subject requests to end treatment.
3. Subjects who fail to collect a minimum of 6 million CD 34 cells/kg body weight at the end of 1st day of Leukapheresis will be either removed or transferred to arm 2 of the protocol after discussion with the PI.

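### The checklist can admit and randomise a subject below partial response who had no salvage, but Section 5.1.1 does not let that subject start vaccination unless partial response is reached in time

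*Combined protocol and SAP*

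**What the plan says.** - **Exclusion 4 (Section 3.2; same wording in Appendix A).** It excludes a subject who did not achieve at least "PR to induction therapy (i.e. VRd) and required salvage induction prior to AHSCT". The two parts are joined, so both must be true.
- **Inclusion 3 (Section 3.1).** It asks only for receipt of the regimen: "Must have received bortezomib, lenalidomide and dexamethasone (VRd) as a form of induction therapy pre-AHSCT". No other inclusion criterion names a response level.
- **Inclusion 9 (Section 3.1).** "No more than 6 months of pre-transplant MM chemotherapy is allowed", counted from the start of induction.
- **Section 5.1.1.** Vaccination may begin after 3 to 6 cycles of VRd, "with a minimum of partial response by IMWG, and at least 2 weeks since the last doses of bortezomib, lenalidomide or dexamethasone".
- **Section 4.0.** "all eligibility criteria do not need to be met until the date of the first study related treatment".
- **Section 4.3.** "During the registration procedures, study personnel are provided the randomization assignment". The Section 7.0 table marks randomisation in the screening column, ahead of the vaccine column.
- **Section 5.6.** It removes subjects who "do not meet the cardiac ejection fraction, pulmonary function test requirement or develop significant organ dysfunction before the transplant admission", and withdraws others for best interest, subject request or insufficient CD34 collection. Response below PR is not named.
- **Section 4.4.** For a subject who receives no assigned treatment, baseline data are collected. Nothing is said about replacement or analysis.

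**The concern.** The list that decides who may be randomised and the rule that decides who may start do not ask for the same response. Where they differ, the subject is already in an arm, and the personnel handling the case have been told which one. Any choice to wait, to give more induction or to take the subject off is then made with the assignment known.

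If the first vaccine is withheld, a group 1 subject has no lymphocyte product collected 7 to 10 days after vaccination, which is the product the experimental strategy depends on. A group 2 subject receives no lymphocyte infusion and loses only the pre-transplant vaccination and the response to it. In either arm the subject no longer fits the planned comparison of post-transplant tetanus responses. Section 10 gives no analysis set or replacement rule that would settle how such a subject is counted.

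**Working it through.** This is a question of logic, and the plan states no figure for it. The four combinations of response to VRd and salvage, set against the two rules, are:

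| Response to VRd | Salvage required | Excluded by exclusion 4? | PR condition of 5.1.1 met? | Rules agree? |
|---|---|---|---|---|
| PR or better | no | no | yes | yes |
| PR or better | yes | no | yes | yes |
| Below PR | yes | yes | no | yes |
| Below PR | no | **no** | **no** | **no** |

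Only the last row conflicts. The next step is to see whether another provision closes it.

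1. *Inclusion criteria.* Inclusion 3 requires VRd to have been given and is silent on the result. It does not close the gap.
2. *Section 4.0.* Eligibility may be completed as late as the first study treatment. For a subject without salvage, PR is not an eligibility criterion, so there is nothing to complete.
3. *Order of events.* Registration on the signed checklist (4.2), assignment during registration (4.3), then vaccination (5.1.1). The response condition is applied after assignment.
4. *Waiting.* A subject below PR at registration could reach PR with further VRd, and 5.1.1 allows up to 6 cycles. Inclusion 9 limits this to six months from the start of induction. The subject is blocked for good only if PR is not reached by then.
5. *Sections 5.6 and 4.4.* Neither names this subject as one to remove, replace or analyse in a given way.

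**Size.** The documents give no rate for the last row, so no expected count can be calculated. What can be stated is the cost per subject: 1/10 = 10% of an arm.

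**Power, as context only.** Section 10.5 states at least 80% power at d = 1.36 with 10 per arm, two-sided 5%, Mann-Whitney test. Scale each group by the Mann-Whitney efficiency 3/π (n′ = n × 3/π) and use a noncentral t with n₁′ + n₂′ − 2 degrees of freedom and noncentrality d × √(n₁′n₂′/(n₁′ + n₂′)).

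- 10 v 10: n′ = 9.549 in each group; noncentrality 1.36 × √4.775 = 2.97; power 0.800. The stated figure reproduces.
- 10 v 9: n′ = 9.549 and 8.594; noncentrality 1.36 × √4.523 = 2.89; power 0.776.

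The second line assumes one subject lost and not replaced. With no such subject, power stays at 0.800. The mismatch does not depend on either figure.

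**The case against.** The strongest reply is that the two sections do different jobs. Section 3 says who may be registered and 5.1.1 says when vaccination can begin, so both apply and a subject below PR simply waits. Section 4.0 sends doubtful cases to the treating physician or principal investigator, registration runs through one coordinator, and the authors may have meant exclusion 4 to cover every response below PR.

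Much of this stands, and it rules out several stronger conclusions that a reader might draw.

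- *That the protocol offers a route to treat below PR.* It does not. Nothing in Section 3 overrides 5.1.1, so vaccinating such a subject would be a deviation. Mixing of response states in the progression-free survival or depth-of-response comparisons does not follow from the text.
- *That the 3-to-6-cycle and two-week conditions are also missing eligibility criteria.* They are timing conditions: the interval is met by waiting, and a subject short of three cycles may continue induction.
- *That the subject can never start.* PR may still be reached within six months.
- *That a count of affected subjects, such as one or two of 20, can be given.* No figure in the documents supports one.
- *That subjects would be handled differently within an arm.* This is possible, but nothing in the documents shows it.

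The reply does not remove the mismatch. A subject who waits and does not reach PR has been randomised with no stated disposition. The presumed intent of exclusion 4 appears in neither Section 3.2 nor the checklist that staff sign.

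**Conclusion.** The point holds as a mismatch between two stated rules. Exclusion 4 and Appendix A let through a subject below PR without salvage; 5.1.1 stops that subject after randomisation unless PR is reached within the limit of inclusion 9. Sections 4.0, 4.4 and 5.6 do not resolve it.

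The conclusion rests on the literal wording of exclusion 4 and on assignment preceding the vaccine, which Section 4.3 and the Section 7.0 table both support. How often it would happen is unknown and could be never. It is worth correcting because the arms are small, the loss would occur with the arm known, and the correction is short. Which response rule is right is a clinical decision for the sponsor and is not judged here.

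**What to change.** - Reconcile exclusion 4, the matching Appendix A item and the PR condition in 5.1.1, so that one response rule, whichever the sponsor intends, governs both registration and the start of vaccination.
- Require that rule to be confirmed and documented before the assignment is released. The allowance in Section 4.0 to complete eligibility by first treatment should not apply to it.
- Leave the cycle-count and two-week conditions in 5.1.1 as timing conditions.
- Do not split exclusion 4 into two separate exclusions unless the sponsor also means to exclude subjects with PR who had salvage. The present text does not exclude them.

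**Cost.** A few words in Sections 3 and 5.1.1 and in Appendix A. A few candidates may become screen failures; Section 5.5 already allows up to 29 screened for 20 enrolled. Baseline disease response is in the Section 7.0 table, but footnote 3 leaves it to physician discretion, so it would have to be documented for every candidate before randomisation.
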